#### 5.1.2 Subject Inclusion Criteria

In order to be eligible for participation in this trial, the subject must:

1. The subject or their legal guardian be willing and able to provide written informed consent for the trial.
2. Be  $\geq 18$  years of age on day of signing informed consent and  $\geq 12$  years of age on day of signing assent.
3. Have histologically confirmed diagnosis of RRP that involves the trachea, lungs, and/or larynx. If a subject is enrolled with laryngeal disease only, the subject must have undergone at least 3 or more surgeries/procedures in any one year to remove the lesions from their larynx. Subjects must have evaluable disease either based on RECIST 1.1 and/or endoscopic parameters, as discussed above.
4. Be required to provide tissue from a newly obtained biopsy of a tumor lesion. *Newly-obtained is defined as a specimen obtained up to 6 weeks (42 days) prior to study registration. Subjects for whom newly-obtained samples cannot be provided (e.g. inaccessible or subject safety concern) may submit an archived specimen only upon agreement from PI.*
5. Have confirmed human papillomavirus-associated lesions based on in-situ hybridization testing and/or polymerase chain reaction which may be performed on a newly obtained biopsy or archived sample.
6. Have a performance status of 0 or 1 on the ECOG Performance Scale.
7. Demonstrate adequate organ function as defined in Table 1, all screening labs should be performed within 28 days of study registration.

*Table 1: Adequate Organ Function Laboratory Values*

SYSTEM	LABORATORY VALUE
Hematological	
Absolute neutrophil count (ANC)	$\geq 1,500 / \text{mcL}$
Platelets	$\geq 100,000 / \text{mcL}$
Hemoglobin	$\geq 9 \text{ g/dL}$ or $\geq 5.6 \text{ mmol/L}$ without transfusion or EPO dependency (within 7 days of assessment)
Renal	
Serum creatinine OR Measured or calculated a creatinine	$\leq 1.5 \times$ institutional upper limit of normal (ULN) OR

*CONFIDENTIAL*

*This document is confidential. Do not disclose or use unless authorized.*

SYSTEM	LABORATORY VALUE
clearance (GFR can also be used in place of creatinine or CrCl)	$\geq 60$ mL/min for subject with creatinine levels $> 1.5 \times$ institutional ULN
Hepatic	
Serum total bilirubin	$\leq 1.5 \times$ institutional ULN OR
	Direct bilirubin $\leq$ institutional ULN for subjects with total bilirubin levels $> 1.5$ institutional ULN

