## **6.0 REGISTRATION PROCEDURES**

### **6.1 GENERAL GUIDELINES FOR DF/HCC INSTITUTIONS**

Institutions will register eligible participants in the Clinical Trials Management System (CTMS) OnCore. Registrations must occur prior to the initiation of protocol therapy. Any participant not registered to the protocol before protocol therapy begins will be considered ineligible and registration will be denied.

An investigator will confirm eligibility criteria and a member of the study team will complete the protocol-specific eligibility checklist.

Following registration, participants may begin protocol therapy. Issues that would cause treatment delays should be discussed with the Overall Principal Investigator (PI). If a participant does not receive protocol therapy following registration, the participant's registration on the study must be canceled. Registration cancellations must be made in OnCore as soon as possible.

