#### **General Guidelines for Other Investigative Sites**

Eligible participants will be entered on study centrally by the Coordinating Center. All sites should call the Coordinating Center to verify slot availabilities.

Following registration, participants should begin protocol treatment within 14 days of registration. Issues that would cause treatment delays should be discussed with the Principal Investigator/Sponsor. If a participant does not receive protocol therapy following registration, the participant's registration on the study must be canceled. The Coordinating Center should be notified of cancellations as soon as possible.

---

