Trial Period:	Screening Phase		Treatment Cycles								End of Treatment (early or at 24 months)	Post-Treatment			
							To be repeated beyond 8 cycles								
Treatment Cycle/Title:	Main Study Screening (Visit 1)	1	2	3	4	5	6	7	8	Discon	Safety Follow-up	Follow Up Visits 	Survival Follow-Up		
Scheduling Window (Days)  :		-28 to -1	$\pm$ 3	$\pm$ 3	$\pm$ 3	$\pm$ 3	$\pm$ 3	$\pm$ 3	$\pm$ 3	At time of Discon	30 days post discon $\pm$ 2 weeks	Every 8 weeks post discon $\pm$ 2 weeks	Every 24 weeks $\pm$ 2 weeks		
should have coagulation factors monitored closely throughout the trial.															
 Laboratory tests for screening are to be performed within 28 days prior to study registration. See Section 10.1.3 for details regarding laboratory tests.															
 After Cycle 1, lab samples can be collected up to 72 hours prior to the scheduled time point. See Section 10.1.3 for details regarding laboratory tests.															
 To be repeated every 4 cycles.															
 The initial tumor imaging will be performed within 28 days prior to study registration. Scans performed as part of routine clinical management are acceptable for use as the screening scan if they are of diagnostic quality and performed within 28 days prior to study registration. The initial tumor imaging study will be performed with intravenous contrast (unless the patient has an allergy to contrast) and subsequent scans will be performed without intravenous contrast.															
 On-study radiographic imaging will be performed every 8 cycles (+/- 14 days) after the first dose of trial treatment. For those patients with pulmonary lesions measurable by RECIST 1.1, lymphadenopathy, or extra-tracheal disease (exception being the larynx), radiographic imaging will be obtained every 4 cycles (+/- 7 days). Per the 3-dimensional tracheal reconstruction volumetric measurement and/or modified RECIST 1.1 used in this protocol, if imaging shows progressive disease, repeat imaging assessment should be performed at a minimum of 4 weeks later in order to confirm progressive disease. Image timing should follow calendar days and should not be adjusted for delays in cycle starts. For patients who have to travel >50 miles for treatment, there will be a window of +/- 7 days for imaging.															

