### **10.1.3 Laboratory Procedures/Assessments**

Details regarding specific laboratory procedures/assessments to be performed in this trial are provided below

---

CONFIDENTIAL

*This document is confidential. Do not disclose or use unless authorized.*

Laboratory Safety Evaluations (Hematology, Chemistry and Urinalysis)

Laboratory tests for hematology, chemistry, urinalysis, and others are specified in Table 5.

---

*CONFIDENTIAL*

*This document is confidential. Do not disclose or use unless authorized.*

Table 5: Laboratory Tests

Hematology	Chemistry	Urinalysis	Other
Hematocrit	Albumin	Blood	Serum $\beta$ -human chorionic gonadotropin†
Hemoglobin	Alkaline phosphatase	Glucose	( $\beta$ -hCG)†
Platelet count	Alanine aminotransferase (ALT)	Protein	PT (INR)
WBC (total and differential)	Aspartate aminotransferase (AST)	Specific gravity	aPTT
Red Blood Cell Count	Lactate dehydrogenase (LDH)	Microscopic exam ( If abnormal )	Total triiodothyronine (T3)
Absolute Neutrophil Count	Carbon Dioxide ‡	results are noted	Free thyroxine (T4)
Absolute Lymphocyte Count	( $CO_2$ or bicarbonate)		Thyroid stimulating hormone (TSH)
	Uric Acid		
	Calcium		
	Chloride		Blood for correlative studies
	Glucose		
	Phosphorus		
	Potassium		
	Sodium		
	Magnesium		
	Total Bilirubin		
	Direct Bilirubin ( If total bilirubin is elevated above the upper limit of normal )		
	Total protein		
	Blood Urea Nitrogen		

† Perform on women of childbearing potential only. ‡ If considered standard of care in your region.

CONFIDENTIAL

*This document is confidential. Do not disclose or use unless authorized.*

Laboratory tests for screening or entry into the Second Course Phase should be performed within 28 days prior to the first dose of treatment. After Cycle 1, pre-dose laboratory procedures can be conducted up to 72 hours prior to dosing. Results must be reviewed by the investigator or qualified designee and found to be acceptable prior to each dose of trial treatment.

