##### **10.1.5.1 Screening**

###### **10.1.5.1.1 Screening Period**

Approximately 28 days prior to study registration, potential subjects will be evaluated to determine that they fulfill the entry requirements as set forth in Section 5.1. Visit requirements are outlined in Section 9.0 – Trial Flow Chart.

Written consent for the main study must be obtained prior to performing any protocol specific procedure. Results of a test performed prior to the subject signing consent as part of routine clinical management are acceptable in lieu of a screening test if performed within the specified time frame. Screening procedures are to be completed within 28 days prior to study registration except for the following:

- For women of reproductive potential, a urine pregnancy test will be performed within 28 days prior to study registration. If urine pregnancy results cannot be confirmed as negative, a serum pregnancy test will be required (performed by the local study site laboratory)

---

*CONFIDENTIAL*

*This document is confidential. Do not disclose or use unless authorized.*

Subjects may be rescreened after initially failing to meet the inclusion/exclusion criteria. Results from assessments performed during the initial screening period are acceptable in lieu of a repeat screening test if performed within the specified time frame and the inclusion/exclusion criteria is met.

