#### **10.1.5.2 Treatment Period**

On-study visits will occur on day 1 of each cycle of Pembrolizumab and will include the following at every visit:

1. Directed physical examination with flexible fiberoptic laryngoscopy and tracheoscopy
2. Review of concomitant medications
3. Vital signs to include temperature, pulse, respiratory rate, weight, and blood pressure.
4. Performance status evaluation
5. Determination adverse events
6. Serum pregnancy test for women of reproductive potential
7. Quality of Life Questionnaires will be done every fourth cycle
8. Laboratory studies: CBC with differential, serum chemistries, liver function tests starting on day 1 of Cycle 2
9. Urinalysis and TSH and Free T4 will be done every fourth cycle
10. CT scans of chest and abdomen will be done during cycle 8
11. Correlative blood collection on Day 1 of each Cycle that corresponds to an operating room visit.

After clinically evident progression the patient will be seen for a study visit, at which the following will be addressed:

1. Directed physical examination with flexible fiberoptic laryngoscopy and tracheoscopy
2. Review of concomitant medications
3. Performance status evaluation
4. Determination adverse events
5. Laboratory studies: CBC with differential, serum chemistries, liver function tests, urinalysis, T3, FT4, and TSH

Fresh tumor specimens will be obtained if feasible during therapy if the patient undergoes examination under general anesthesia and/or debridement for a standard-of-care clinical purposes per the study flow chart.

---

*CONFIDENTIAL*

*This document is confidential. Do not disclose or use unless authorized.*

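### Screening organ-function labs are timed to registration in three places and to first dose in a fourth, so results can be up to 42 days old at dose 1 under one rule and 28 under the other; separately, the albumin cut-off carries a unit that makes it ineffective

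*Combined protocol and SAP*

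**What the plan says.** **Timed to registration.** Section 5.1.2, item 7: "Demonstrate adequate organ function as defined in Table 1, all screening labs should be performed within 28 days of study registration". Section 9.1, footnote 10: "Laboratory tests for screening are to be performed within 28 days prior to study registration"; that footnote then sends the reader to Section 10.1.3 for detail. Section 10.1.5.1.1: "Screening procedures are to be completed within 28 days prior to study registration".

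**Timed to first dose.** Section 10.1.3: "Laboratory tests for screening or entry into the Second Course Phase should be performed within 28 days prior to the first dose of treatment".

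**From registration to treatment (Section 6.1).** For sites outside DF/HCC: "Following registration, participants should begin protocol treatment within 14 days of registration". For DF/HCC institutions: "Following registration, participants may begin protocol therapy", with no number of days.

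**Next organ-function labs.** Section 10.1.5.2 lists, for on-study visits, "Laboratory studies: CBC with differential, serum chemistries, liver function tests starting on day 1 of Cycle 2".

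**Albumin.** Table 1 in Section 5.1.2 requires a value above 2.5 mg/dL. Hemoglobin in the same table is in g/dL (or mmol/L). Section 10.1.5.5 points back to Section 5.1.2 for organ function at entry to the Second Course Phase.

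**The concern.** Table 1 is the laboratory gate for a drug whose dose-modification table lists liver and kidney toxicity. The plan gives two reference dates for the age of those results. The dates coincide only if treatment starts on the day of registration.

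Two things are at stake. The first is consistent eligibility: a monitor or auditor using 5.1.2 and another using 10.1.3 can reach opposite answers on the same patient. The timing of the checks adds to this. The eligibility checklist is completed before registration (Section 12.1.2), when the dosing date may not yet be fixed, so only the registration rule can be fully verified then. The second is the baseline for safety, which is a primary objective. If the last result before dose 1 is old and the next scheduled one is at Cycle 2, an abnormality found at Cycle 2 is harder to assign to the drug or to the patient's earlier condition.

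The albumin entry is a separate matter. It is an operative eligibility cut-off, and the printed unit leaves it with no effect.

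**Working it through.** The documents state no maximum lab age, so there is no figure of the plan's own to reproduce. The check is calendar arithmetic.

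**Inputs**
- Lab draw to registration, d: at most 28 days (5.1.2 item 7; footnote 10; 10.1.5.1.1).
- Registration to first dose, g: at most 14 days at sites outside DF/HCC, worded as a should; no stated limit at DF/HCC institutions (6.1).
- Lab draw to first dose under 10.1.3: at most 28 days.
- First on-treatment blood count, chemistry and liver tests: Day 1 of Cycle 2 (10.1.5.2).

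**Age at first dose = d + g**

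| Rule followed | Sites | Maximum age at dose 1 |
|---|---|---|
| Registration anchor only | Outside DF/HCC | 28 + 14 = 42 days |
| Registration anchor only | DF/HCC, assumed g = 7, 14, 21, 28 | 35, 42, 49, 56 days |
| First-dose anchor (10.1.3) | All | 28 days |

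The DF/HCC gaps are assumptions that show the range. No visit window is added to any figure.

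**When the two rules disagree.** The registration rule passes if d ≤ 28. The first-dose rule passes if d + g ≤ 28. They give opposite answers when d ≤ 28 < d + g. With g = 14, that means every draw made 15 to 28 days before registration, the earlier half of the screening window. For example, d = 20 and g = 14 gives 34 days: acceptable under 5.1.2, out of window under 10.1.3.

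**Is there a fresh draw before dose 1?** Section 10.1.5.2 starts these tests at Cycle 2. The flow chart is broken in the available text but is consistent with this. The blood count row in 9.1 has 10 marks for 1 + 8 + 1 + 1 = 11 columns (screening, eight cycles, discontinuation, safety visit). If screening, discontinuation and the safety visit are marked, 10 − 3 = 7 marks remain for eight cycles. The point rests mainly on 10.1.5.2.

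**Comparisons within the plan.** Inclusion 8 also times pregnancy testing to registration, but it points to a further test within 72 hours of any dose; inclusion 7 has no such pointer. For retreatment, Section 9.2 footnote 15 counts back from the first retreatment dose and so agrees with 10.1.3. The timing conflict is confined to initial treatment.

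**Albumin.** 1 g = 1,000 mg, so 2.5 mg/dL = 2.5 / 1,000 = 0.0025 g/dL.

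**The case against.** The strongest reply is that the windows are compatible. A site can satisfy both, and one that follows the whole protocol must. Dosing on results older than 28 days then breaches 10.1.3. This stands, and it limits the point: a reader might infer that the protocol as a whole permits dosing on 42-day-old labs, and it does not. The 42 days arise only where a site works from the registration-anchored sections. Three places state that anchor, and one of them is the eligibility criterion itself.

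There are other safeguards at dose 1. Section 10.1.3 has results reviewed and accepted before every dose, Section 11.5.4 asks for assessment of possible events of clinical interest, including lab results, before each dose, and exclusion 14 covers current laboratory abnormalities at the investigator's judgement. These stand, but none requires a new organ-function sample before dose 1. It would also be wrong to read the plan as requiring no laboratory test at the first dose: women of reproductive potential need a serum pregnancy test within 72 hours of it.

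At DF/HCC sites, the missing limit might be read as lab age without any cap. Section 10.1.3 still caps it, treatment delays go to the Overall PI, and the mandatory registration SOP is not among the documents, so it may set a limit.

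A reader might extend the argument to thyroid results or to the rule that stops the study when more than 30% discontinue for adverse events. Neither extension is supported. Table 1 has no thyroid criterion, on-study thyroid tests run every fourth cycle, and nothing in the documents shows that up to 14 extra days of lab age would move the discontinuation rate. Nor is attribution impossible: a baseline before dosing exists, and Table 6 also uses time course, other causes, dechallenge and rechallenge.

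On albumin, sites may well recognise the misprint and apply the intended unit. The documents do not say so, and the criterion is what an auditor would check.

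**Conclusion.** The conflict is real and modest in size. Under the registration anchor, results can be up to 42 days old at dose 1 at sites outside DF/HCC, and older at DF/HCC sites if the start slips further. Under 10.1.3 the limit is 28 days everywhere. The difference is up to 14 days at outside sites. This is a worst case, not a typical age. It assumes that a draw at the edge of the screening window is used, that the 14-day should is followed, and that 10.1.3 is overlooked.

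The supported consequences are inconsistent eligibility decisions and a weaker baseline for judging Cycle 2 abnormalities. The Simon two-stage figures are not affected.

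The albumin entry is a wrong figure in an operative criterion, for initial and Second Course entry alike. That it excludes no one assumes only that no living patient has serum albumin at or below 0.0025 g/dL.

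**What to change.** 1. State one laboratory window, in the same words, in Section 5.1.2 item 7, Section 9.1 footnote 10, Section 10.1.3 and Section 10.1.5.1.1. The sponsor chooses the anchor. If more than one window is meant to apply, each section should say so.
2. Reconcile the registration-to-treatment wording for DF/HCC and other sites in Section 6.1, or explain why it differs.
3. Correct the albumin unit in Table 1 after checking the sponsor's source for the threshold. The correction carries through to Section 10.1.5.5 by its cross-reference.

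The cost is amendment wording, an updated eligibility checklist and, for patients whose start slips, an occasional repeat of a routine blood test, which 10.1.3 already implies.

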### 5.1.3 Subject Exclusion Criteria

The subject must be excluded from participating in the trial if the subject:

1. Is currently participating and receiving study therapy or has participated in a study of an investigational agent and received study therapy or used an investigational device within 4 weeks of the first dose of treatment.
2. Has a known diagnosis of immunodeficiency or is receiving systemic steroid therapy or any other form of immunosuppressive therapy within 7 days prior to study registration.
3. Has a known history of active TB (Bacillus Tuberculosis)

*CONFIDENTIAL*

*This document is confidential. Do not disclose or use unless authorized.*

4. Has a known hypersensitivity to pembrolizumab or any of its excipients.
5. Has had a prior anti-cancer monoclonal antibody (mAb) within 4 weeks prior to study registration or who has not recovered (i.e.,  $\leq$  Grade 1 or at baseline) from adverse events due to agents administered more than 4 weeks earlier.
6. Has had prior chemotherapy, targeted small molecule therapy, or radiation therapy within 2 weeks prior to study registration or who has not recovered (i.e.,  $\leq$  Grade 1 or at baseline) from adverse events due to a previously administered agent.

**NOTE:** *Subjects with  $\leq$  Grade 2 neuropathy are an exception to this criterion and may qualify for the study.*

7. Recovery from effects of any major surgery or significant traumatic injury at least 28 days before the first dose of study treatment. Endoscopic debridement of RRP lesions is NOT considered a major surgery
8. Has a known diagnosis of invasive squamous cell carcinoma within the past 2 years.
9. Patients with invasive squamous cell carcinoma derived from their RRP who are not considered appropriate for surgery, radiation therapy, or chemotherapy by their treating oncology team may be considered eligible for the study.
10. Has active autoimmune disease that has required systemic treatment in the past 2 years (i.e. with use of disease modifying agents, corticosteroids or immunosuppressive drugs). Replacement therapy (eg., thyroxine, insulin, or physiologic corticosteroid replacement therapy for adrenal or pituitary insufficiency, etc.) is not considered a form of systemic treatment.
11. Has a history of (non-infectious) pneumonitis that required steroids or current pneumonitis.
12. Evidence of interstitial lung disease.
13. Has an active infection requiring systemic therapy.
14. Has a history or current evidence of any condition, therapy, or laboratory abnormality that might confound the results of the trial, interfere with the subject's participation for the full duration of the trial, or is not in the best interest of the subject to participate, in the opinion of the treating investigator.
15. Has known psychiatric or substance abuse disorders that would interfere with cooperation with the requirements of the trial.
16. Is pregnant or breastfeeding, or expecting to conceive or father children within the projected duration of the trial, starting with the pre-screening or screening visit through 120 days after the last dose of trial treatment.

---

CONFIDENTIAL

*This document is confidential. Do not disclose or use unless authorized.*

17. Has received prior therapy with an anti-PD-1, anti-PD-L1, or anti-PD-L2 agent.
18. Has a known history of Human Immunodeficiency Virus (HIV) (HIV 1/2 antibodies).
19. Has known active Hepatitis B (e.g., HBsAg reactive) or known active Hepatitis C (e.g., HCV RNA [qualitative] is detected).
20. Has received a live vaccine within 30 days of planned start of study therapy.

**NOTE:** *Seasonal influenza vaccines for injection are generally inactivated flu vaccines and are allowed; however intranasal influenza vaccines (e.g., Flu-Mist®) are live attenuated vaccines, and are not allowed.*

